9.4 TRANSFER OF SAMPLES

Local laboratories will be used for the analyses of FBC, biochemistry analysis, viral serologies and autoimmune profiles.

Central laboratories

Hammersmith (qPCR)

pPCR for BCR-ABL and pPCR for WT1 (Hammersmith) – all patients, all time points. For shipment from Southampton and Exeter this shipment will be taken by next day delivery post in Royal Mail safeboxes. Samples will be processed in the molecular haematology laboratory, Hammersmith Hospital, [name].

Royal Mail safeboxes will be provided by the UoSCTU to investigators at participating sites. If further supplies are required, please contact the WIN Clinical Trial Coordinator at UoSCTU.

Southampton (Immunological)

Immunological analyses for vaccine responses, including leukapheresis samples and bone marrow samples, will be processed and frozen locally according to agreed SOP and stored in liquid nitrogen. Sample transport to the Cancer Sciences Division, Southampton, in dry ice and using a temperature logger will be undertaken once a sufficient number or samples have been collected locally (Hammersmith, Exeter).

9.5 ASSESSMENT OF EFFICACY

In CML the primary endpoint of the study will be molecular responses of BCR-ABL transcripts by qPCR which will be done centrally at the Hammersmith ([name]) in a Clinical Pathology Accredited (CPA) accredited MRD laboratory. This is an accepted and routine test for monitoring of this disease. We intend to monitor this at every visit to the end of the study and we know already that fluctuations on stable tyrosine kinase inhibitors, notably imatinib, are very small (less than 0.5 log over 1 year). WT1 qPCR is to be undertaken in these patients in parallel also at every time point from the same blood sample using the standardised WT1 qPCR assay recently reported by Cilloni et al (JCO 2009).

We will measure only WT1 transcripts in patients with AML (vaccination group, control group) at every follow up visit.

The molecular monitoring will allow us to assess efficacy of the vaccine over time and also give us effectiveness data on the size of the biological effect.

Immunological efficacy and mechanism evaluation of the vaccine is intended to the completion of study for each patient by measuring the increase in WT1 specific CD8 T cells over time, compared to baseline. For this we will use ELISPOT and/or tetramer analysis for WT1 in conjunction with T cell memory, activation and differentiation markers (such as but not limited to CD3, CD4, CD8, CD45RA, CCR7 + 'dump channel'; with appropriate controls).

Additional immunological analyses (research tests) that will be undertaken, depending on availability of material:

CD4 and CD8 responses to WT1 and control antigens by ELISPOT or intracellular cytokine/tetramer analysis by flow cytometry, cytotoxicity studies of patient derived T cells against either CML/AML cells or appropriate surrogate targets, phenotyping of blood B cell and NK/NKT cell numbers and phenotype. It is likely that evaluation will use other tumour derived and non-tumour derived antigen as controls antigens. Examples for this are CMV, Flu, HIV, or PRAME, PASD-1 ecc.

Given the funding envelope the study is begun under it is expected that the duration of the immunological evaluation of the study will extend beyond the evaluation of the primary endpoints and secondary endpoints. Immunological evaluation is also a rapidly changing field in which the tools are improved and newly developed quickly. To reflect this, in the consent form patients will be asked to permit this later use of material for additional immunological evaluations beyond the submission of the end of study report to the regulatory bodies.

9.6.1 MOLECULAR RESPONSE:

Definition of BCR-ABL Response

- For patients with a baseline BCR-ABL transcript level less than 11: CMR: 0 BCR-ABL transcript level with ABL control copy greater than or equal to 32,000; in TWO CONSECUTIVE tests. These patients cannot be assessed for a major or minor response as defined below.
- 2) For patients with a baseline BCR-ABL transcript level greater than or equal to 11:
 - a. CMR: 0 BCR-ABL transcript level with ABL control copy greater than or equal to 32,000; in TWO CONSECUTIVE tests.
 - b. Major response: a fall greater than 1 log in the BCR-ABL transcript level ratio.*
 - c. Minor response: a fall greater than 0.5 log in the BCR-ABL transcript level ratio.*

*Confirmed in an ABL control copy greater than or equal to 32,000 in two consecutive samples at any time during follow up.

Definition of WT1 Response

1) For patients with a baseline WT1/GUS ratio less than 0.1%:

CMR: 0% WT1/GUS ratio with GUS control copy greater than or equal to 32,000; in TWO CONSECUTIVE tests.

These patients cannot be assessed for a major or minor response as defined below.

- 2) For patients with a baseline WT1/GUS ratio greater than or equal to_0.1%:
 - a. CMR: 0% WT1/GUS ratio with GUS control copy greater than or equal to 32,000; in TWO CONSECUTIVE tests.
 - b. Major response: a fall greater than 1 log in the WT1/GUS ratio.*
 - c. Minor response: a fall greater than 0.5 log in the WT1/GUS ratio.*

*Confirmed in a GUS control copy greater than or equal to 32,000 in two consecutive samples at any time during follow up.

9.6.2 IMMUNOLOGICAL RESPONSE:

Definition of validated assay by ELISPOT response:

A positive response using the validated assays by ELISPOT will be determined by having all of the following criteria:

- More than 25 spots per million Peripheral Blood Mononuclear Cell (PBMC) assay;
- (increase in spot number exceeds spot number at baseline + 2 x standard deviation at baseline;
- p-value from the t-test (post-baseline time point vs baseline time point) < 0.05.

Immunological response may also be assessed by ICS and/or tetramer staining. Only results produced by validated assays will be used in the analysis.

All patients, who are removed from the study for reasons other than progressive disease, will be reevaluated at the time of treatment discontinuation.

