4.4 WITHDRAWAL CRITERIA

Patients who are removed from the study treatment due to adverse experiences (clinical or laboratory) will be treated and followed according to accepted medical practice. All pertinent information concerning the outcome of such treatment must be recorded in the CRF.

Patients who withdraw their consent from participating in the trial will be withdrawn from protocol procedures. Data that has been collected on these patients to this timepoint will be included in the analyses.

The discontinuation of study treatment will occur under the following circumstances

- Unacceptable toxicity
- Any patient who experiences a WHO CTC grade 3 adverse reaction (AR), possibly or likely to be related to vaccination will discontinue further vaccination.
- Severe local toxicity (CTC 3 or greater) at the site of injection, development of clinically relevant anti-DNA antibodies or rheumatoid factors, clinical or biochemical evidence of muscle destruction (CTC 3 or greater) or other unexpected toxicity will lead to termination of the vaccination of that patient.

- Unforeseen events: any event which in the judgement of the Investigator makes further treatment inadvisable
- SAE requiring discontinuation of treatment
- The patient withdraws consent where a patient is not evaluable, additional patients will be recruited to replace them (See Section 3.1)
- Serious violation of the study protocol (including persistent patient attendance failure and persistent non-compliance)
- Evidence of disease progression
- In patients with CML requirement to discontinue or change the dose of tyrosine kinase inhibitor therapy

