5 TREATMENTS

HLA A2-ve patients will receive standard care in accordance with accepted medical practice.

HLA A2+ patients will receive the treatment described in Sections 5.1 to 5.6:

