10 STATISTICS AND DATA ANALYSIS

10.1 SAMPLE SIZE CALCULATION

10.1.1 SAMPLE SIZE CALCULATION FOR CML

The sample size calculation is based on A'Hern's Single-Stage Design and the primary outcome measure of molecular response (BCR-ABL or WT1).

A molecular response (BCR-ABL or WT1) rate of 20% would imply the vaccine clearly warrants further investigation. A molecular response rate of 5% or less would be unacceptable and would indicate the vaccine does not warrant further investigation. The probability of obtaining a false positive result, α (i.e. incorrectly accepting for further study a treatment that has a true PFS rate 30%) is set at 10%. The probability of a false negative result, β (i.e. incorrectly rejecting for further study a treatment with a true PFS rate of 50%) is set at 10%. Using these parameters, $\alpha = 0.1$, $\beta=0.1$, p0=5%, p1=20%, 32 HLA A2+ve patients need to be recruited to the study. The drop-out rate is expected to be less than 10%, hence a total of 36 patients will be recruited.

This trial needs to observe a minimum of 4 out of 32 patients who are molecular responders in order to provide evidence that the vaccine warrants further investigation. Patients will be followed up for 2 years to assess molecular response.

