10.2 ANALYSIS PLAN

Molecular Analysis

The analyses on molecular response will be performed on all patients with molecular data at a minimum of 2 post-baseline time points (HLA A2 positive patients must also have received at least 1 dose of the vaccine).

Immunological Analysis

To be evaluable for immunological response, positive HLA A2 patients must receive at least 1 dose of the vaccine and the immunological testing must be available until at least week 8 post first dose.

Safety Analysis

For safety analyses, all patients with positive HLA A2 status who received at least one study drug administration will be evaluable for toxicity. All controls will be included in the safety analyses, where relevant.

Other Analysis

For all other analyses, an intention to treat principle will be used.

10.2.1 ANALYSIS FOR CML PATIENTS ONLY:

Primary:

The primary endpoint is molecular response of BCR-ABL (major or minor response or CMR). For the purpose of analysis, response (as defined by section 9.6) will be measured at weeks 4, 8, 12, 16, 20, 32 and 11, 17 and 23 months. Fisher's exact test will be used to compare differences in proportions of molecular response in CML patients versus controls.

Secondary:

The primary analysis will be repeated for major response or CMR of BCR-ABL.

The analysis methods used for BCR-ABL will be repeated for WT1.

Progression free survival, duration of response and overall survival (as defined in Section 2.2) will be estimated using the method of Kaplan and Meier for each group. Survival estimates will be presented with 90% confidence intervals. These endpoints will also be compared between the CML patients and controls using log-rank tests.

Progression free survival for CML patients is defined in Section 2.2 and is measured as the time from date of consent to the study to date of progression or death from any cause. Alive patients who are progression free will be censored at their date of last follow up. Similar analysis will be performed for overall survival and duration of response.

Toxicity will be collected and evaluated according to the NCI CTC toxicity scale (v4.0) and compared between the vaccinated and control groups by Fisher's exact test.

10.2.2 ANALYSIS FOR AML PATIENTS ONLY:

Primary:

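### The CML primary endpoint has three conflicting response windows, and no passage stops a BCR-ABL fall after a TKI change from counting as a vaccine response

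*Protocol*

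**What the plan says.** **Window.** Three sections of the Protocol govern when a CML molecular response can occur.

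- Section 9.6.1 defines major and minor responses as falls of more than 1 log and more than 0.5 log in the BCR-ABL ratio, with the footnote "Confirmed in an ABL control copy greater than or equal to 32,000 in two consecutive samples at any time during follow up". Section 9 follows patients for up to 36 months from consent, and the schedule marks qPCR through month 36.
- Section 10.1.1: "Patients will be followed up for 2 years to assess molecular response".
- Section 10.2.1, for the purpose of analysis, says response "will be measured at weeks 4, 8, 12, 16, 20, 32 and 11, 17 and 23 months".

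**TKI changes.** Section 5.6 requires the TKI dose to stay unchanged. Section 4.4 lists, among the reasons for stopping study treatment, "In patients with CML requirement to discontinue or change the dose of tyrosine kinase inhibitor therapy". Sections 11.2 and 11.4 keep patients given alternative treatment in the trial for follow-up and data analysis. Section 2.2.1 makes time to next CML treatment a secondary endpoint, so new CML drugs during the study are foreseen. The molecular analysis set in 10.2 is every patient with molecular data at two or more post-baseline time points; vaccinated patients also need at least one dose.

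**Controls.** Section 5 states "HLA A2-ve patients will receive standard care in accordance with accepted medical practice" and assigns Sections 5.1 to 5.6 to HLA A2-positive patients.

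**Basis for stability.** Section 9.5 says that fluctuations on stable TKI therapy, "notably imatinib, are very small (less than 0.5 log over 1 year").

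**The concern.** The primary endpoint should identify one set of samples from which each patient is called a responder or not. Here the set depends on which section is followed. The trial is open label, so a choice made after results are known would be open to challenge.

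The second problem is attribution. The design takes 5% as the response rate at which the vaccine is not worth pursuing. A fall produced by a change of TKI or by a new CML drug says nothing about the vaccine, yet the text as written counts it. Confirmation in two consecutive samples guards against assay noise but not against this, because a fall on altered therapy can be sustained.

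At stake is the go decision, which rests on four responders among 32 vaccinated patients and makes no use of the controls. The comparison with controls is exposed as well if TKI changes differ between the arms.

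**Working it through.** **1. Which samples count.**

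| Source | Last time point | Samples admitted |
|---|---|---|
| 9.6.1 with Section 9 | month 36 | any two consecutive |
| 10.1.1 | 2 years | not specified |
| 10.2.1 | month 23 | weeks 4, 8, 12, 16, 20, 32; months 11, 17, 23 |

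After week 20, the 10.2.1 list leaves out these scheduled qPCR visits up to month 24: week 22, weeks 24–28, week 34, month 14, month 17 day 14, month 20 and month 24. This changes the meaning of consecutive:

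- On the list, months 17 and 23 are adjacent. On the visit schedule, month 17 day 14 and month 20 lie between them.
- Falls at months 17 and 23 with a value back above the threshold at month 20 are confirmed on the list but not on the schedule.
- Falls at months 20 and 23 only are confirmed on the schedule but not on the list.

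Visits 2 and 5 (weeks 2 and 10) are not done in HLA A2-negative patients. An any-sample reading therefore gives the vaccinated arm two more qPCR samples than the controls.

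**2. Whether a fall after a TKI change counts.** Section 4.4 ends vaccination. Sections 11.2 and 11.4 keep the patient in follow-up and analysis. The analysis set in 10.2 has no exclusion, and 9.6.1 has no cut-off. The closing sentence of 9.6.2, on re-evaluating patients removed from the study, sets none either. As written, the fall counts.

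**3. The plan's own design.** Inputs from 10.1.1: "p0=5%, p1=20%, 32 HLA A2+ve patients need to be recruited to the study", both error rates 10%, and at least 4 responders of 32.

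The exact binomial search for the smallest n with P(X ≥ r | 0.05) ≤ 0.10 and P(X ≥ r | 0.20) ≥ 0.90 returns n = 32, r = 4, as stated.

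- False go: P(X ≥ 4 | 32, 0.05) = 1 − (0.1937 + 0.3263 + 0.2662 + 0.1401) = 0.074
- Power: P(X ≥ 4 | 32, 0.20) = 0.907

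**4. Sensitivity to responses not due to the vaccine.** Let b be the probability of such a response in a patient who would not otherwise respond. The documents give no value; 0 to 10% is an assumed range. The null rate becomes p = 1 − (1 − 0.05)(1 − b).

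| b (assumed) | p | P(X ≥ 4 of 32) |
|---|---|---|
| 0 | 0.0500 | 0.074 |
| 1% | 0.0595 | 0.120 |
| 2% | 0.0690 | 0.176 |
| 3% | 0.0785 | 0.241 |
| 5% | 0.0975 | 0.381 |
| 10% | 0.1450 | 0.701 |

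As a head count: if exactly one of the 32 is certain to respond for a non-vaccine reason, the other 31 need three, and P(X ≥ 3 | 31, 0.05) = 0.201. If two are certain, P(X ≥ 2 | 30, 0.05) = 0.446.

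**The case against.** **The operative window may already be clear.** Section 10.2.1 is the analysis section and applies the 9.6 definition at listed times ending at month 23, which fits the 2 years of 10.1.1. On that view the 36-month reading is the weakest, and leaving visits off the list is a choice. This has force. But the phrase in 9.6.1 is part of the endpoint definition that 10.2.1 invokes, and the protocol does not say whether consecutive means adjacent on the list or on the visit schedule.

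**TKI changes may be rare and seldom produce a fall.** Entry requires 24 months of maintained cytogenetic response with no TKI change or dose modification in the previous year, and 5.6 asks for a constant dose. A dose reduction or stop would not be expected to lower transcripts. A patient switched for rising transcripts must first make up that rise and then fall below study baseline. All of this limits the frequency, which is unknown, but none of it sets a rule.

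**Controls absorb shared trends.** The Fisher comparison in 10.2.1 largely removes drift common to both arms. That stands for drift. It does not remove TKI changes that differ between arms, and it plays no part in the 4-of-32 rule.

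**Stronger readings that the documents do not support:**

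- *Slow molecular drift makes the null response rate large.* Section 9.5 bounds fluctuation over one year; it states no downward trend. Simulating an assumed fall of 0.2 log a year in every patient with an assay SD of 0.15 gives about 10% on the 10.2.1 list and about 25% on all visits to month 24. Without the assumed trend the rate is about 1% or less. The result comes from the assumption.
- *Controls may change TKI freely.* Section 5 says only that they receive standard care, and the synopsis says without arm limit that CML patients continue TKI therapy. What can be said is that the unchanged-dose rule is stated under the sections for vaccinated patients.
- *A baseline averaged over two samples is needed.* Section 9.6.1 refers only to baseline; its derivation can be left to the analysis plan.

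**Conclusion.** The point holds on the text. The CML primary endpoint has conflicting windows. Falls after a TKI change or a new CML drug count as responses, because the patient remains in the analysis and nothing excludes the later samples. The effect may also differ between arms.

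The 4-of-32 design is computed correctly, but its margin is thin. About one extra percentage point of non-vaccine response takes the false-go probability from 0.074 to 0.120, above the stated 10%; five points take it to 0.381. These values assume independent patients and that 5% is the right null rate for whichever window applies. They show how sensitive the rule is. A reader might infer that the trial's actual false-go rate is 0.38 or more, but the documents give no rate of TKI change or of falls after one, so that does not follow.

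Every stated window is longer than the one year covered by the stability figure. That is a reason to fix the window and to show an earlier rate as well. It is not evidence that the 5% null rate is wrong.

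**What to change.** Use one rule in 9.6.1, 10.1.1 and 10.2.1:

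1. **One window**, ending no later than month 24, with one list of visits common to both arms. State that consecutive refers to that list.
2. **One rule for altered CML therapy, in both arms.** In the primary analysis, samples taken after the first TKI change, TKI dose change or new CML drug do not count. A patient with no confirmed response before then is a non-responder.
3. **A sensitivity analysis** that counts all samples in the window regardless of TKI changes.
4. **Optional:** report the 12-month response rate beside the primary rate, since 12 months is the span the stability figure covers.

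The cost is amendment or analysis-plan wording, ideally settled before response data are reviewed. The data are already collected: qPCR is scheduled at these visits in both arms, and the date and type of subsequent treatments are recorded under Section 9. The downside is small: a few late or post-switch responses are not counted. This is an analysis rule only and changes nothing in how patients are treated.

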4 SELECTION AND WITHDRAWAL OF PATIENTS

4.1 INCLUSION CRITERIA

CML patients:

Philadelphia chromosome positive CML in chronic phase, in complete cytogenetic response (CCyR) but with detectable BCR-ABL transcripts and maintained the CCyR on tyrosine kinase inhibitor monotherapy for a minimum of 24 months

AML patients:

Patients with WT1+ AML complete remission (CR) post chemotherapy or AML in morphologic CR with incomplete blood count recovery (CRi) defined as patients who fulfil all of the criteria for CR except for residual neutropenia (<1,000/ μ L) or thrombocytopenia (<100,000/ μ L).

As the vast majority of AML express WT and evaluation in CR or CRi is technically not feasible, formal demonstration of WT1 expression in AML cells is not required. Where historical or relapsed samples become available, WT1 expression status will be evaluated post hoc.

All patients:

- ≥ 18 years of age,
- Written informed consent
- WHO Performance status of 0 or 1.
- For vaccination groups: HLA-A0201 positive in at least one allele
- For control groups: HLA A2 negative in both alleles
- Renal function and liver function (Creatinine <1.5 x upper limit of normal, liver function tests < 1.5 x upper limit of normal); Lymphocyte count 
> 1.0 x10⁹/l*; normal clotting
- HB>100 g/l
- Adequate venous access for repeated blood sampling according to protocol schedule.
- If sexually active and possibly fertile, patients must agree to use appropriate contraceptive methods during the trial and for six months afterwards.

* If the lymphocyte count is below 1.0 at the time of entry into the trial but has been over 1.0 in the last 6 months and has also not declined rapidly in the days and weeks preceding entry, then the patient is eligible.

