The primary endpoint is time to disease progression measured as the time from date of consent to the study to date of progression or death from any cause (progression is defined as disease relapse). Alive patients who are progression free will be censored at their date of last follow up. Progression free survival will be estimated using the method of Kaplan and Meier for each group. Survival estimates will be presented with 90% confidence intervals. A log rank test will be computed to compare AML patients and their controls.

Secondary:

The primary analysis will be repeated for survival time.

A secondary endpoint is molecular response of WT1 (major or minor response or CMR). For the purpose of analysis, response (as defined in section 9.6) will be measured at weeks 4, 8, 12, 16, 20, 32 and 11, 17 and 23 months. Proportions of responders in the vaccinated group will be compared with the control group using Fisher's exact test for the CML and AML groups. This analysis will be repeated for major molecular response or CMR of WT1.

Toxicity will be collected and evaluated according to the NCI CTC toxicity scale (v4.0) and compared between the vaccinated and control groups by Fisher's exact test.

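### Section 9.6.1 can count a patient whose WT1/GUS ratio was already 0% at baseline as a WT1 complete molecular responder, although nothing changed

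*Protocol*

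**What the plan says.** Section 9.6.1 splits patients by baseline WT1/GUS ratio. The lower group is defined by "For patients with a baseline WT1/GUS ratio less than 0.1"%, with no lower limit, so it contains 0%. Its only response is "CMR: 0% WT1/GUS ratio with GUS control copy greater than or equal to 32,000; in TWO CONSECUTIVE tests". On the finer grades the protocol says: "These patients cannot be assessed for a major or minor response as defined below". That closes major and minor response to this group and leaves CMR open.

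Sections 2.2.1 and 2.2.2 list WT1 response, including CMR, as a secondary endpoint in both cohorts. Section 10.2.2 repeats it for AML: "A secondary endpoint is molecular response of WT1 (major or minor response or CMR"), compared between vaccinated and control patients by Fisher's exact test. Section 10.2.1 applies the BCR-ABL methods to WT1 in CML.

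The molecular analysis set in section 10.2 reads: "The analyses on molecular response will be performed on all patients with molecular data at a minimum of 2 post-baseline time points". Vaccinated patients must also have had one dose. Baseline WT1 is not mentioned.

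On entry, section 4.1 admits "Patients with WT1+ AML complete remission (CR) post chemotherapy" or with incomplete count recovery, and adds that "formal demonstration of WT1 expression in AML cells is not required". CML patients must be "in complete cytogenetic response (CCyR) but with detectable BCR-ABL transcripts". That is a condition on BCR-ABL, not on WT1.

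**The concern.** Major and minor response are changes: a fall of more than 1 log or 0.5 log from baseline. CMR is a level. A level works as a response criterion only if the patient did not already meet it at the start. For BCR-ABL, eligibility largely secures this, since section 4.1 requires detectable transcripts and section 4.2 excludes CMR. For WT1 nothing does so in either cohort, and the AML cohort enters in remission.

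Three results are at stake. The absolute WT1 response rate could include patients in whom nothing happened. The comparison of vaccinated with control patients would lose contrast, because the same patients are added in both arms. And objective 3 in section 2, which correlates molecular with immunological response, would have unchanged patients on the responder side. The planned repeat analysis restricted to major response or CMR does not help, because CMR still counts there.

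**Working it through.** **Reading the rule.** Three baseline values, each followed by two consecutive 0% results with adequate GUS:

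- Baseline 0.1% or above: CMR, a true fall.
- Baseline above 0% but below 0.1%: CMR, a true fall.
- Baseline 0%: CMR, no fall.

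Only the third is a problem, and sections 2.2, 4.1, 4.2, 9.6.1 and 10.2 contain nothing that removes it.

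**The plan's own figures.** The protocol states no expected rate, sample size or power for WT1 response in AML. Its two A'Hern designs reproduce by exact binomial calculation: AML 16 of 39 (30% against 50%) has alpha 0.094 and power 0.900; CML 4 of 32 (5% against 20%) has alpha 0.074 and power 0.907. The AML design is on progression-free survival at 2 years and does not involve WT1.

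**Effect on the reported rate.** Inputs, all assumptions because the protocol gives none of them:

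- f: share of patients at 0% at baseline, shown as a range.
- s = 0.90: proportion of those who later show two consecutive zeros.
- p = 0.05: true response rate in the other patients.

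Reported rate = f × s + (1 − f) × p.

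| f | calculation | reported rate |
|---|---|---|
| 0% | 0 + 0.05 | 5% |
| 2% | 0.018 + 0.049 | 6.7% |
| 10% | 0.090 + 0.045 | 13.5% |
| 20% | 0.180 + 0.040 | 22% |
| 30% | 0.270 + 0.035 | 30.5% |

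The result depends on p as well. With p = 20% and f = 10% the reported rate is 0.09 + 0.18 = 27%, and 0.09/0.27, one third, of the responders were negative at entry.

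**Effect on the contrast.** If f and s are the same in both arms, the term f × s cancels and the difference becomes (1 − f) × (p_vaccinated − p_control). A true difference of 30% − 5% = 25 points becomes 24.5 points at f = 2%, 22.5 at 10%, 20 at 20% and 17.5 at 30%. Power falls faster than the difference, because both rates also rise and so does their variance.

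An illustration with 39 patients per arm, a two-sided 5% level and every baseline zero persisting (s = 1), all assumed since the protocol fixes no control-group size. Exact Fisher power with no baseline zeros is 0.81.

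| f | power, present wording | power, baseline zeros excluded |
|---|---|---|
| 10% | 0.54 | 0.74 (35 per arm) |
| 20% | 0.37 | 0.66 (31 per arm) |
| 30% | 0.27 | 0.55 (27 per arm) |

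In this illustration, excluding baseline zeros gives more power than keeping them, although the denominator shrinks.

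**The case against.** The strongest objection is that the documents do not show the problem occurs. No figure is given for the share at exactly 0%, and there is reason to think it could be small: sections 1.3 and 7.1.8 say that some normal CD34+ cells express WT1 at low level, so remission does not imply a zero reading. The section 4.1 statement on WT1 expression concerns antigen positivity of the leukaemia for eligibility. It shows that there is no entry rule; it does not show that patients enter at 0%. This stands. A reader might infer that the WT1 rate is inflated, or would mostly describe who entered negative. The protocol supports neither, only that the rule can produce this.

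A second objection is that the analysis plan could settle the handling. That is weaker. The protocol itself defines response, and an analysis that follows the definition as written gives the wrong classification. It is true that section 10.2 fixes only the analysis set; the numerator comes from 9.6.1.

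Three stronger readings also need to be set aside:

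- **The CML go/no-go rule is compromised.** Section 10.1.1 words its outcome as BCR-ABL or WT1, so baseline WT1 zeros might seem to count towards the 4 of 32. But sections 2.1.1 and 10.2.1 name BCR-ABL alone as primary. The wording of 10.1.1 is a separate inconsistency.
- **BCR-ABL CMR has the same gap.** CML entry requires detectable transcripts and excludes CMR, and no problem with the primary endpoint has been quantified.
- **The rule favours the vaccine.** It is identical in both arms. It would favour one arm only if the share at 0% differed between the HLA groups, and the protocol gives no basis for assuming so.

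**Conclusion.** The point holds as a defect in a definition. As written, 9.6.1 scores an unchanged 0% patient as a WT1 complete molecular responder, and no other section prevents it.

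The size cannot be derived. With a 5% true rate and 90% persistence it runs from no effect at f = 0 to a reported rate of 30.5% at f = 30%, and other inputs would give other figures. The expected effects are higher absolute rates in both arms, a diluted comparison, and misclassified responders in the correlation with immune response. WT1 response is secondary in both cohorts. The AML primary endpoint and its 16 of 39 rule are unaffected, as is the CML primary endpoint as sections 2.1.1 and 10.2.1 define it. The change is worth making because it is cheap and the defect is certain, even though its effect is not.

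**What to change.** In section 9.6.1:

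- Require a baseline WT1/GUS ratio above 0% for a patient to be assessable for WT1 response.
- Take patients with a 0% baseline out of both numerator and denominator of the WT1 response rate.
- Report those patients separately by arm, as remained negative or became positive.
- State the number assessable for WT1 response in each arm.

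Two limits keep the change narrow. Do not require a baseline GUS count of at least 32,000 from patients with measurable WT1, since that would drop patients in whom a fall can be observed. Do not extend the exclusion to BCR-ABL, since that would alter the CML primary analysis set.

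The cost is a change of wording and a smaller WT1-evaluable denominator. No new data are needed: section 9.1 already schedules WT1 qPCR before treatment in both cohorts.
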